#### 7.7.3 *Adverse Events*

Treatment-emergent adverse events (TEAEs) are defined as those AEs with onset after the first dose of study drug or existing events that worsened after the first dose during the study. Treatment-emergent AEs will be summarized by dose group. Events reported with a partial onset date (e.g., month and year are reported but the day is missing) will be considered to be treatment-emergent if it cannot be confirmed that the event onset was prior to the first dose of study drug based on the available date entries.

Verbatim terms on case report forms will be mapped to preferred terms, preferred terms and system organ classes using MedDRA, version 23.0.

Summaries that are displayed by system organ class and preferred terms will be ordered by descending incidence of system organ class and preferred term within each system organ class. Summaries of the following types will be presented:

- Number of TEAEs, number and percentage of subjects with at least one TEAE and number and percentage of subjects with TEAEs by MedDRA system organ class and preferred term;

- Number of treatment-emergent SAEs (TESAEs), number and percentage of subjects with at least one TESAE and number and percentage of subjects with TESAEs by MedDRA system organ class and preferred term;
- Number of treatment-related TEAEs, number and percentage of subjects with at least one related TEAE and number and percentage of subjects with related TEAEs by MedDRA system organ class and preferred term. Summary will be presented for TEAEs related to LOAd703, TEAEs related to atezolizumab and TEAEs related to either drug;
- Summary by relationship (related to LOAd703, related to atezolizumab, related to LOAd703 and/or atezolizumab and not related to LOAd703 or atezolizumab) and CTCAE grade including: Number of TEAEs, number and percentage of subjects with at least one TEAE and number and percentage of subjects with TEAEs by MedDRA system organ class and preferred term. Events in each relationship category will be counted only once using the highest CTCAE grade.

At each level of summarization (e.g., any AE, system organ class, and preferred term), subjects experiencing more than one TEAE will be counted only once.

Related events include those reported with a causality to LOAd703 and/or atezolizumab of “Possible”, “Probable” or “Definite”; events considered not related are those reported as “Unlikely” or “Unrelated”.

Adverse event data (including any AEs starting before first study drug) will be presented in data listings by subject, dose group, and event. Serious AEs and AEs leading to withdrawal, interruption, or dose reduction of the study drug will be presented in separate data listings. Lowest level terms will be listed in addition to preferred terms.

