## 5.5 Dose Limiting Toxicity (DLT)

As LOAd703 will be dose escalated, the patients will be monitored for dose limiting toxicity (DLT). DLT is defined as any grade 3 or higher toxicity (CTCAE Version 5.0) that is attributed (definitely, possibly or probably) to LOAd703. A DLT attributed to LOAd703 will lead to dose reduction (see 5.6.8 *LOAd703 Dose Modifications*).

Phase I: The first patient on each dose level must have been evaluated for DLT [REDACTED] before patient 2 and 3 in the same cohort can start treatment. Patient 2 and 3 should start treatment at least 24 hours apart.

All 3 patients in the cohort must have been evaluated for DLT before decision on dose escalation is taken for the next cohort.

Phase II: Patient enrollment continues and evaluation for DLTs [REDACTED] (see 10.2 *Sample Size*).

Toxicity attributed to atezolizumab will not be assessed as DLTs in the study but can still lead to dose modifications (see 5.7.7 *Atezolizumab Dose Modifications*).

If a patient experiences an AE grade 3 or higher that can be attributed to the LOAd703 injection procedure (i.e., a bacterial infection, injection site pain, etc.), to disease, or another unrelated cause, it is not a DLT. SAEs due to injection procedure can lead to change of injection procedure (such as change of lesion) instead of treatment discontinuation, depending on the type of AE and the risk of recurrence of the AE.

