### **9.2.2 Attribution Definitions**

The Investigator will attempt to assess the relationship of the event to the study drugs separately. An AE is considered to be associated with the use of any or both of the investigational products if the attribution is determined as possible, probable or definite. Attribution of AEs will be recorded in the CRF as:

- **Unrelated**: The AE is clearly NOT related to LOAd703 (or atezolizumab).
- **Unlikely**: The AE is doubtfully related to LOAd703 (or atezolizumab).
- **Possible**: The AE may be related to LOAd703 (or atezolizumab).
- **Probable**: The AE is likely related to LOAd703 (or atezolizumab).
- **Definite**: The AE is clearly related to LOAd703 (or atezolizumab).

Attribution will be specified for LOAd703, atezolizumab, treatment procedure (i.e., intratumoral injection and/or intravenous infusion), disease or other.

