## 5 STUDY OBJECTIVES

### 5.1 Primary Study Objective

The primary objective of this study is to determine the tolerability of LOAd703 given by intratumoral (i.t.) injection(s) in combination with intravenous (IV) atezolizumab.

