#### ***6.4.1 Description of Safety Variables***

##### ***6.4.1.1 Dose Limiting Toxicities***

As LOAd703 will be dose escalated, the subjects will be monitored for dose limiting toxicity (DLT). DLT is defined as any grade 3 or higher toxicity according to the NCI CTCAE version 5.0 that is attributed (definitely, possibly, or probably) to LOAd703. A DLT attributed to LOAd703 will lead to dose reduction.

[REDACTED] Subjects 2 and 3 should start treatment at least 24 hours apart.

All 3 subjects in the cohort must have been evaluated for DLT before decision on dose escalation is taken for the next cohort.

Toxicity attributed to atezolizumab will not be assessed as DLTs in the study but can still lead to dose modifications.

If a subject experiences an AE grade 3 or higher that can be attributed to the LOAd703 injection procedure (i.e., a bacterial infection, injection site pain, etc.), to disease, or another unrelated cause, it is not a DLT. Serious AEs (SAEs) due to injection procedure can lead to a change of injection procedure (such as change of lesion) instead of treatment discontinuation, depending on the type of AE and the risk of recurrence of the AE.

[REDACTED]

[REDACTED]

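### SAP 7.7.3 classifies adverse events by the two drugs only, so harm attributed solely to the treatment procedure is summarised with disease events and no planned table identifies it

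*SAP*

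**What the plan says.** SAP 5.1 sets the primary objective as the "tolerability of LOAd703 given by intratumoral (i.t.) injection(s) in combination with intravenous (IV) atezolizumab". The protocol objective (3.1) has the same content, and the primary endpoint in both documents is safety by CTCAE v5.0.

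Protocol 9.2.2 fixes what is collected on cause: "Attribution will be specified for LOAd703, atezolizumab, treatment procedure (i.e., intratumoral injection and/or intravenous infusion), disease or other". The same section says that attribution goes into the CRF. It sets out five levels, from Unrelated to Definite, worded in terms of LOAd703 or atezolizumab.

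SAP 7.7.3 fixes what is summarised. An event is related if its causality to one or both drugs is Possible, Probable or Definite. The related-TEAE summary is produced for LOAd703, for atezolizumab and for either drug. The table by grade is defined as "Summary by relationship (related to LOAd703, related to atezolizumab, related to LOAd703 and/or atezolizumab and not related to LOAd703 or atezolizumab". The procedure appears in none of these definitions. Protocol 10.3 also describes related events for the two drugs only.

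The DLT rule in SAP 6.4.1.1 covers toxicity "that is attributed (definitely, possibly, or probably) to LOAd703". It then treats procedure events separately: "If a subject experiences an AE grade 3 or higher that can be attributed to the LOAd703 injection procedure", or "to disease, or another unrelated cause, it is not a DLT". Protocol 5.5 states the same rule.

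**The concern.** The route is part of what the trial is judging. LOAd703 is given by percutaneous intratumoral injection up to 12 times, so complications of the needle are part of the burden of the treatment as given. Both documents expect such events. They name bacterial infection and injection site pain as examples, and they allow a serious procedure event to change how the injection is done.

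The protocol collects the attribution needed to describe these harms, but the SAP's classification has no place for it. All results are descriptive (SAP 7.1.1 and 7.6.5.1), so what a reader learns about tolerability depends heavily on how the tables sort events. A reader looking at the unrelated-to-either-drug rows would see procedure harms and disease events mixed together, and could take both as background.

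**Working it through.** The point concerns classification, so the check is to follow an event through the stated rules.

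**The plan's own figures.** The only figures tied to attribution are the DLT boundaries. With target φ = 0.3 and the usual BOIN defaults φ1 = 0.6φ = 0.18 and φ2 = 1.4φ = 0.42 (assumed, since the documents do not state them):

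- Escalation: ln[(1−φ1)/(1−φ)] / ln[φ(1−φ1)/(φ1(1−φ))] = ln(0.82/0.70) / ln(0.246/0.126) = 0.2365.
- De-escalation: ln[(1−φ)/(1−φ2)] / ln[φ2(1−φ)/(φ(1−φ2))] = ln(0.70/0.58) / ln(0.294/0.174) = 0.3585.

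Both match the plan. All 27 table cells (9 sample sizes × 3 rules) also reproduce; the elimination row assumes a uniform prior and a 0.95 posterior cut-off. These figures are sound and the point does not depend on them.

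**Where an event goes under SAP 7.7.3**

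| Attribution recorded | Related-TEAE summary | Table by relationship and grade |
|---|---|---|
| LOAd703 at least Possible | LOAd703; either drug | LOAd703; either drug |
| Procedure, and LOAd703 at least Possible | LOAd703; either drug | LOAd703; either drug |
| Procedure only | Not included | Unrelated to either drug |
| Disease only | Not included | Unrelated to either drug |

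The last two rows are identical, so the planned relationship categories cannot separate a procedure-only event from a disease event. The second row sets the limit of the point: an event that is also at least Possible for a drug is counted as related. The SAP does not mention procedure events by name here; the result follows from its definitions.

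**Whether another planned output separates them**

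- All-cause TEAE table: the event is counted, but not by cause.
- Treatment-emergent SAE table: the event is counted if serious. As described, this table is not split by relationship.
- Listings (SAP 7.7.3 and 7.7.4): the event appears by subject, with lowest level and preferred terms. The text does not say whether procedure attribution is displayed, and the output templates are not available here.
- DLT summary (SAP 7.7.2): the event is not included, under the rule quoted above.

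**Whether redaction explains the gap.** Parts of SAP 6.4.1.1 and 7.7.2 are blacked out, but SAP 7.7.3, which defines the relationship tables, shows no redaction.

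**Whether the SAP departs from the protocol.** It does not, because Protocol 10.3 is also limited to the drugs. The gap lies between what Protocol 9.2.2 collects and what either document plans to summarise.

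**The case against.** The strongest reply is that nothing is hidden. Procedure events stay in the all-cause and serious-event tables, in the unrelated rows by grade and in the listings. Preferred terms would often reveal the cause, as with injection site pain. With at most 50 patients enrolled, listings can be read in full. The unrelated label is also literally true, since it refers only to the two drugs, and the SAP does what Protocol 10.3 asks.

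All of that stands, and it limits the point to one missing aggregation. It does not remove it. Terms such as infection, bleeding or pain do not show whether the needle or the tumour was the cause. A patient-level rate by grade and dose group would have to be rebuilt by hand from listings, if they show the attribution at all.

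A reader might infer three stronger things that the documents do not support:

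- *That keeping procedure events out of DLTs is an error.* It is an explicit rule, the same in both documents, with its own handling of serious procedure events.
- *That every injection harm is reported as unrelated.* This holds only where neither drug is rated at least Possible.
- *That a sizeable share of patients is affected.* An assumed grade 3 or higher risk of 1% to 2% per injection, independent across 12 injections, gives 1 − 0.99^12 = 11% to 1 − 0.98^12 = 22%. The same risks over 4 injections give 1 − 0.99^4 = 4% to 1 − 0.98^4 = 8%. The documents give neither a complication rate nor an expected number of injections (12 is a maximum), and the calculation also assumes that every event is procedure-only.

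**Conclusion.** The point holds as a reporting gap on the primary endpoint. Attribution to the procedure is collected, no visible planned table uses it, and the relationship categories put procedure-only TEAEs together with disease and other causes. The frequency of these events by grade and dose group therefore cannot be read from any planned summary.

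No numerical size is claimed. The conclusion rests on the visible text of SAP 7.7.3 and Protocol 9.2.2, and it would weaken if the unseen output templates already summarise events by procedure attribution. It does not affect the DLT definition, the escalation boundaries or the choice of MTD.

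**What to change.** In SAP 7.7.3:

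1. Keep all existing drug-only rows, so that nothing already specified is lost.
2. In the related-TEAE summary and the table by CTCAE grade, add a row *related to treatment procedure*, with injection and infusion shown separately if the CRF distinguishes them, and a row *related to LOAd703, atezolizumab and/or procedure*. Give the treatment-emergent SAE table the same breakdown, which would be new there.
3. Limit the final *not related* row to events attributed to none of the three, and relabel it accordingly.
4. State the cut-off for counting an event as procedure-related. Protocol 9.2.2 words its five levels for the two drugs and does not say that the same scale applies to the procedure.
5. Record the change in SAP 7.9, or in the CSR if the SAP is already final.

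The cost is table programming, a check of how the CRF holds the procedure field, and one decision on the cut-off. No new data are needed if the field was collected as the protocol describes. Counts in the new combined row can only equal or exceed those for either drug, so the text should say that this reflects a wider definition.

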#### **7.7.4      Deaths, Other Serious Adverse Events, and Other Significant Adverse Events**

All deaths during the study, including the post treatment follow-up period, will be listed by subject, to include the primary cause of death. Serious AEs and other significant AEs, including those that led to withdrawal, interruption, or dose reduction of the study drug, will be provided in separate subject data listings.

#### **7.7.5      Clinical Laboratory Evaluation**

All descriptive summaries of laboratory results will be based on data analyzed by local laboratories and presented in Système International (SI) units, as suggested by the Center for Biologics Evaluation and Research and the Center for Drug Evaluation and Research *Position on Use of SI Units for Lab Tests* (Oct 2013). All data will be included in by-subject data listings. Laboratory measurements identified as abnormal (i.e., outside the normal range) will also be listed separately by subject, laboratory test, and unit. In

addition, normal ranges provided by each local laboratory will be presented in a separate listing.

Clinical laboratory measurements, including serum chemistry (██████████) and hematology, will be summarized by dose group. Descriptive statistics will be presented for observed values and changes from baseline at each visit where parameters were scheduled to be collected per the clinical study protocol.

Values reported as greater than or less than some quantifiable limit (e.g., “< 1.0”) will be summarized with the sign suppressed in summary tables and figures, using the numeric value reported. Data will display on subject listings to include the sign.

Where applicable, hematology and chemistry results for select parameters will be assigned a toxicity grade based on NCI CTCAE version 5.0. If the quantitative criteria for grading are equivalent for two grades and the differentiation is described by clinical interventions, the clinical intervention component will not be considered and the highest CTCAE grade will be assigned. Similarly, death related to AE (i.e., grade 5) cannot be determined with available laboratory-based data collection and, thus, will not be summarized as a category. Laboratory parameters that include multiple sets of criteria for each direction (██████████) will be summarized separately to reflect each set of criteria.

Five-by-five contingency tables will be presented for lab tests where toxicity grading can be applied, to summarize the shift from the baseline grade to the worst post-baseline grade. Grades will be presented as none (grade 0; i.e., measurements did not meet any CTCAE criteria for grades 1 through 4), mild (grade 1), moderate (grade 2), severe (grade 3), or life-threatening (grade 4). Summary results will include the count and percentage of subjects within each shift category.

#### **7.7.6      *Vital Signs, Physical Examination Findings, and Other Observations Related to Safety***

##### **7.7.6.1      *Vital Signs***

Vital sign parameter measurements will be summarized by dose group. Descriptive statistics will be presented for results and change from ██████████. Measurements taken relative to the LOAd703 injection will be tabulated separately to those taken relative to the atezolizumab infusion. ██████████ data will be listed only (unless ██████████).

#### 7.7.6.2 *ECOG Performance Status*

ECOG performance status will be summarized by dose group. Descriptive statistics will be presented for observed values and changes from [REDACTED] at each visit where ECOG performance status was scheduled to be collected. The number and percentage of subjects with each score at each visit will also be presented by dose group.

#### 7.7.6.3 *12-Lead Electrocardiogram*

Results of the 12-lead ECG will be presented in subject data listings by subject, study visit, and parameter. The overall assessment by the investigator will also be listed.

#### 7.7.6.4 *Physical Examination*

Results of the physical examination will be presented in subject data listings by subject, study visit, and body system.

#### 7.7.6.5 *Prior and Concomitant Medications*

Medications will be coded using the World Health Organization Drug Dictionary (WHODD), September 1st 2019 version. Medications entered on the eCRF will be mapped to Anatomic Therapeutic Chemical (ATC) drug class (level 4) and drug name.

Prior and concomitant medications will be summarized separately, and the study phase of each medication will be determined programmatically based on medication start and end dates. A prior medication is defined as any medication administered prior to the date of the first dose of study drug. A concomitant medication- is defined as any medication administered on or after the date of the first dose of study drug. A medication may be defined as both prior and concomitant. If it cannot be determined whether a medication was received prior to the start of study drug dosing due to partial or missing medication start and/or end dates, it will be considered a prior medication. Likewise, if it cannot be determined whether a medication was received after the start of study drug dosing, it will be considered concomitant.

For both prior and concomitant medications summaries, the number and percentage of subjects receiving any medication will be summarized by dose group, as will the number and percentage receiving any medication by ATC drug class and generic drug name. Prior medications will also be summarized over all subjects combined (total). Subjects reporting use of more than one medication at each level of summarization (any medication received, ATC class, and generic drug name) will be counted only once. ATC class terms will be displayed by descending order of incidence, as will generic drug names within each ATC class. The study phase during which each medication was received (e.g., prior, concomitant, or both) will be presented on the listing of prior and concomitant medications.

#### 7.7.6.6 *Concomitant Medical or Surgical Procedures*

Concomitant procedures will be listed only.

### 7.8 **Determination of Sample Size**

#### 7.8.1 *Safety*

The study will be conducted using a BOIN design with a target DLT rate of 0.3. This design has algorithmic escalation/de-escalation rules like a traditional 3+3 design but allows for specification of the target DLT rate and expanded accrual beyond N=6 with continued consistent toxicity monitoring (i.e., the assessment of DLT rate continues throughout the study which gives a well-defined safety evaluation of Phase I/II studies).

Two LOAd703 dose levels will be tested together with a fixed dose of atezolizumab. The BOIN design allows for enrollment of 3 subjects in a cohort and the number of subjects with DLT determines whether additional subjects are treated with the current dose or if the dose is decreased or increased. In general, the dose will be escalated if the observed toxicity rate at the current dose is  $\leq 0.2365$ , and the dose will be de-escalated if the observed toxicity rate at the current dose is  $\geq 0.3585$ . If the observed toxicity rate is between 0.2365 and 0.3585, 3 additional subjects will be treated at the current dose. For cohorts of size 3, the decision boundaries are shown below. Additional cohorts will be added in the unlikely event that more than N=25 participants at a single dose level are needed.

Number of Subjects Treated in a Defined Cohort	3	6	9	12	15	18	21	24	25
Escalate dose if number of DLT $\leq$	0	1	2	2	3	4	4	5	5
Treat additional 3 subjects at current dose if number of DLT =	1	2	3	3, 4	4, 5	5, 6	5-7	6-8	6-8
De-escalate dose if number of DLT $\geq^*$	2	3	4	5	6	7	8	9	9
Eliminate** dose level and all higher doses from further use if number of DLT $\geq$	3	4	5	7	8	9	10	11	12

\* At the lowest dose level, if the recommendation is to de-escalate and the dose level has not been eliminated from consideration, 3 additional subjects can be accrued at the same dose level; otherwise, the trial will be stopped.

\*\* Note that if the DLT level reaches the elimination limit, this dose level is abandoned from the study independently of DLT events at lower dose levels.

[figure not shown]
### 7.8.2 Efficacy

### 7.9 Changes in the Conduct of the Study or Planned Analyses

Section 10.3 of the protocol describes summaries of urinalysis

There were no other changes to the study conduct or planned analyses identified within the development of this SAP, relative to the descriptions provided within the clinical study protocol.

